---

## PROTOCOL AMENDMENT SUMMARY OF CHANGES TABLE

DOCUMENT HISTORY	
Document	Date of Issue
Original Protocol	[25-Feb-2021]
Protocol 2.0	[20-Jan-2023]

## 1 PROTOCOL SUMMARY

### 1.1 Synopsis

**Protocol Title:** Gene profile in *EGFR*m locally advanced or metastatic NSCLC patients post Osimertinib 1L treatment failure: A real-world, multi-center study (GPS)

**Short Title:** Gene profile post Osimertinib 1L failure

#### Rationale:

Osimertinib is a potent, oral, irreversible tyrosine kinase inhibitor (TKI) of *EGFR* mutation (*EGFR*m)-positive and T790M mutation-positive forms of *EGFR* with demonstrated clinical activity on central nervous system (CNS) metastases. Osimertinib is designed to have limited activity against wild-type (WT) *EGFR*. Osimertinib is approved globally, and marketed as Tagrisso®, for the first-line treatment of patients with locally advanced or metastatic NSCLC whose tumours have *EGFR* exon 19 deletions (ex19del) or exon 21 (L858R) substitution mutations and the treatment of patients with locally advanced or metastatic *EGFR* T790M mutation-positive NSCLC whose disease has progressed on or after *EGFR* TKI therapy. It has been approved as first-line treatment for advanced *EGFR* mutated NSCLC in China, and has also been widely used in clinical practice no matter in the first-line or in the later-line.

While similar to 1/2 G *EGFR*-TKI, acquired resistance to Osimertinib invariably often develops with a median PFS of 19 months[1]. The characterization of the landscape of resistance enables the development of subsequent therapies, but mechanisms of resistance to Osimertinib is primarily derived from patients who received Osimertinib after other *EGFR*-TKIs, such as *EGFR* C797, *EGFR* G724, *EGFR* L792, *MET* amplification, and so on[2-5]. Prior reports of acquired resistance mechanisms to Osimertinib primarily focus on patients who received Osimertinib as the second-line treatment. However, the mechanisms of resistance to Osimertinib in the first-line treatment are far from being clearly explored. As Osimertinib in the first-line treatment is applied more and more widely in advanced *EGFR*m+ NSCLC patients, we urgently need to know the resistance mechanisms to guide subsequent treatment strategy. Until now, the largest study to explore acquired resistance mechanism to 1L Osimertinib was FLAURA study, which detected 91 paired plasma samples by next generation sequencing (NGS) . The most common acquired resistance mechanisms were *MET* amplification (15%) and *EGFR* C797X mutation (7%)[6]. The result was quite different from the study conducted by Adam J. Schoenfeld et al using tissue (N=27), with squamous transformation accounting for 15% and *MET* amplification 7%[7]. The reason for different results maybe because these two studies used different samples to analyse resistance mechanisms, and the above two detection methods may have different sensitivity and specificity. In addition, Schoenfeld et al study was limited to patients at one site, Memorial Sloan Kettering Cancer Center in NY, USA.

Although some small sample studies have reported the possible resistance mechanisms of Osimertinib in the first-line treatment, it is still an urgent need to explore the whole gene profile

in *EGFR*m advanced NSCLC patients post Osimertinib 1L treatment by paired tissue and plasma to guide subsequent treatment strategy[6, 7]. Thus, the gene profile post Osimertinib 1L treatment in tissue and plasma may help to guide the following treatment.

MET overexpression is key resistance mechanism after 1L Osimertinib failure[8]. SAVANNAH observed improved outcomes in post 1L Osimertinib resistant *EGFR*m NSCLC patients with MET IHC90+(≥90% tumour cells MET IHC3+) and/or FISH10+(MET gene copy number ≥10); the estimated prevalence of IHC90+ is 29% in SAVANNAH study published on 2022 WCLC [9]. MET amplification is also a key resistance mechanism after 1L Osimertinib failure[8]. FISH is golden standard testing method for MET amplification. The prevalence of FISH 5+(MET gene copy number ≥5 and/or MET/CEP7≥2) in INSIGHT 2 study [10] is 33% and the prevalence of FISH10+ in SAVANNAH study is 20% [9]. The prevalence data of MET amplification by FISH testing and MET overexpression by IHC testing in Chinese advanced *EGFR*m NSCLC patients who had disease progression following 1L osimertinib are very limited and still need further explore.

Tissue was unavailable for some advanced *EGFR*m NSCLC patients who had disease progression following 1L Osimertinib and blood samples show high potential as an alternative sample [11]. ddPCR is as an alternative technique with high sensitivity and specificity for MET amplification testing and it has been explored in previous study[12]. Besides, ddPCR blood assay for MET amplification testing still need be further validated through concordance of MET amplification between FISH testing in tissue and ddPCR testing in plasma.

## Objectives and Endpoints

Objectives	Endpoints
Primary	
To describe the gene profile in EGFR m advanced NSCLC patients post Osimertinib 1L treatment.	

Gene profile in tissue

 
Gene profile defined as gene alteration detected by NGS and frequency of every gene alteration.
 
All gene alterations include gene mutation, copy number variation(CNV), fusion, etc.
 
The frequency of all gene alteration detected by NGS(%) = (number of patients with every gene alteration detected by NGS)/(total number of patients in the FAS)×100%.

Secondary	

Objectives	Endpoints
To assess the concordance of plasma and tissue	

Gene profile in plasma Gene profile defined as gene alternation detected by NGS and frequency of every gene alternation.

Concordance of plasma and tissue Using selected representative genes (for example EGFR, MET, PIK3CA and etc.) to measure the concordance Concordance of Gene X in plasma and tissue is defined as sensitivity, specificity, positive predictive value (PPV) and negative predictive value (NPV) between plasma and tissue results., Tissue sample is the reference standard.

sensitivity=(number of patients with positive result in both plasma and tissue)/(total number of patients with positive result in tissue samples)×100%;

specificity=(number of patients with negative result in both plasma and tissue)/(total number of patients with negative result in tissue samples)×100%.

PPV (%)=(number of patients with positive result in both plasma and tissue)/(total number of patients with positive result in plasma samples)×100%;

NPV (%)=(number of patients with negative result in both plasma and tissue)/(total number of patients with negative result in plasma samples)×100%;

The percentage of pathology transformation Pathology transformation is defined as those transformation from non-small-cell lung cancer to small-cell lung cancer or from adenocarcinoma to squamous carcinoma, can be observed by IHC

CCI

Objectives

Endpoints

- CCI

## Overall Design

**Disclosure Statement:** This is a real-world, multi-centre prospective study elucidating the gene profile in *EGFR*m locally advanced or metastatic NSCLC patients post Osimertinib 1L treatment.

### **Participant Population:**

The target population of interest in this study is participants with locally advanced or metastatic

NSCLC, harboring common *EGFR*m of ex19del/L858R and having evidence of disease progression following 1L Osimertinib.

### **Number of Participants:**

Approximately 200 participants in *EGFR*m locally advanced or metastatic NSCLC with the evidence of disease progression following 1L Osimertinib will be enrolled and 15 sites will be involved to elucidate the gene profile in paired tissue and plasma so that approximately 180 participants whom would be get gene profile, assuming a 10% drop-out.

**Note:** "Enrolled" means a participant's, or their legally acceptable representative's, agreement to participate in a clinical study following completion of the informed consent process. Potential participants who are screened for the purpose of determining eligibility for the study, but are not randomly assigned/assigned in the study, are considered "screen failures", unless otherwise specified by the protocol.

### **Human Biological Sample Analysis:**

Participants will be required to provide paired tissue and whole blood after disease progression following 1L Osimertinib. 200 tissue samples and 200 whole blood samples will be used to detect gene alteration by NGS, respectively. 200 tissue samples will be used to detect pathological transformation by IHC. Approximately 80-100 tissue samples will be used to test MET overexpression by MET IHC and MET amplification by FISH respectively. Approximately 80-100 whole blood samples will be used to test MET amplification by ddPCR.

## **Statistical methods**

### **General Aspects**

A Statistical Analysis Plan (SAP) will be prepared and finalised prior to database lock. All statistical analyses will be completed using SAS version 9.4 or later. Descriptive statistics will be provided for all variables, as appropriate. Continuous variables will be summarized by the number of observations, mean, standard deviation, median, interquartile range (Q1, Q3), minimum, and maximum. Categorical variables will be summarized by frequency counts and percentages for each category. The 95% confidence interval (CI) will be calculated as appropriate.

The primary, secondary **CCI** will be based on Full analysis set (FAS), which will include all patients who meet the required inclusion/exclusion criteria and have valid gene data from both plasma and tissue. FAS will be used for the analyses of all data collected.

The Data Cut-off (DCO) date of the primary endpoint, gene profile in tissue, will be when all participants have completed their gene testing in tissue and whole blood and got their testing

results. The Data Cut-off (DCO) date is expected to be approximately 12 weeks after LSI. The primary objective is to describe the gene profile in *EGFR*m advanced NSCLC patients after progression on 1L Osimertinib treatment. Gene profile in tissue will be analyzed by NGS method. All gene alterations in tissue(e.g., gene mutation, amplification, deletion, fusion, etc.) detected by NGS will be observed. Proportion of Gene X alteration(%) = (number of patients with Gene X, which is an example of a certain gene)/(total number of patients in the FAS)×100%. Some cases which patients have more than one gene alteration need to be considered.

The secondary objective is to assess gene profile in plasma, concordance of plasma and tissue and the percentage of pathology transformation will be analysed by NGS method and IHC respectively. All gene alterations in plasma(e.g., gene mutation, amplification, deletion, fusion, etc.) detected will be observed. Proportion of Gene X alteration(%) = (number of patients with Gene X, which is an example of a certain gene)/(total number of patients in the FAS)□100%. Some cases which patients have more than one gene alteration need to be considered. Using selected representative genes (for example *EGFR*, MET, PIK3CA and etc.) to measure the concordance. Concordance of Gene X in plasma and tissue is defined as sensitivity, specificity, positive predictive value (PPV) and negative predictive value (NPV) between plasma and tissue results. Tissue sample is the reference standard. Sensitivity=(number of patients with positive result in both plasma and tissue)/(total number of patients with positive result in tissue samples)□100%; Specificity=(number of patients with negative result in both plasma and tissue)/(total number of patients with negative result in tissue samples)□100%. PPV (%)=(number of patients with positive result in both plasma and tissue)/(total number of patients with positive result in plasma samples)□100%; NPV (%)=(number of patients with negative result in both plasma and tissue)/(total number of patients with negative result in plasma samples)□100%.

Pathology transformation defines as pathological type of lung cancer change, which will be confirmed by pathologists. Number and percentage of patients with pathology transformation will be summarized. Proportion of pathology transformation(%) = (number of patients with pathology transformation)/(total number of patients in the FAS)□100%.

Two analyses are planned. The first interim analysis data cut-off (DCO) point will happen when 100 patients have completed their gene testing in tissue and whole blood and got their testing results(50% maturity). The final analysis is planned for when the last patient has completed their gene testing in tissue and whole blood and got their testing results.

CCI

CCI

[figure not shown]
- 
- 
- 
- 
- 
- 
- 
- 

## 1.2 Schema

**Figure 1** Study Design

## Study Design A Real World, Multicenter Study

RECIST 1.1=Response Evaluation Criteria in Solid Tumors, Version 1.1.  
NSCLC, non-small cell lung cancer; EGFR, epidermal growth factor receptor.

### 1.3 Schedule of Activities

The procedures for this study are presented in the SoA (Table 1).

**Table 1** **Schedule of Activities**

Procedure	Screening and Data Collection		Notes	Details in CSP Section or Appendix
Visit	1			
Informed consent a	X			Sections 5.1
Inclusion and exclusion criteria	X			Section 5.1 and 5.2
Diagnostic clinical procedures				
Histology	X			
Clinical stage with lymph node and distant metastasis at diagnosis and post 1L Osimertinib	X			
Record documented common EGFR mutation results by an accredited laboratory through ARMS, Super-ARMS, and NGS testing b	X			
Routine clinical procedures				
Demography and smoking history c	X			Section 7.2.1
Physical examination and weight(Kgs)	X			Section 7.2.1
Height(CMs)	X			Section 7.2.1
Medical history and comorbid conditions d	X			Sections 5.1 and 5.2
WHO/ECOG performance status post Osimertinib 1L treatment	X			Section 7.2.2
Osimertinib Efficacy measurements				
Duration of 1L Osimertinib treatment e	X			
Best response of 1L Osimertinib	X			
Progression pattern post 1L Osimertinib	X			
Genetic analysis				

Procedure	Screening and Data Collection		Notes	Details in CSP Section or Appendix
Mandatory screening tumour tissue sample (archived or newly acquired biopsy) for Central NGS testing and central MET FISH testing; local IHC testing (included MET overexpression by MET IHC and SCLC pathology transformation by IHC)	X			Section 7.3.1
Mandatory screening blood sample (newly acquired; 2*10ml) for Central NGS testing and central ddPCR MET amplification testing	X			Section 7.3.1 and Appendix C

a Written informed consent and any locally required privacy act document authorisation must be obtained prior to performing any protocol-specific procedures, including screening/baseline evaluations.

b Participants are eligible to be considered for inclusion on the basis of local pre-existing *EGFR* tumour tissue or plasma testing results by molecular testing.

c Include date of birth or age, gender, race, and ethnicity for all participants.

d Include any treatment history before enrolling the study, complication and related history(chronic diseases which require treatment currently)

e Include the start and end dates of 1L Osimertinib treatment; starting dose,

Note: Data collection following study analysis until the end of the study is described in Section 7.

Note: The screening visit will confirm that the patients will be receiving a biopsy (scheduled for after enrolment), but they will not actually receive a biopsy at the screening visit.  
CSP=Clinical Study Protocol; ECOG=Eastern Cooperative Oncology Group; ICF=informed consent form; WHO=World Health Organisation

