### **Type of Participant and Disease Characteristics**

- 4 Pathologically confirmed non-small cell lung cancer (NSCLC) with documented *EGFR* sensitive mutation (*EGFR* 19del and L858R) positive before Osimertinib 1L.
- 5 Locally advanced (clinical stage IIIB, IIIC) or metastatic NSCLC (clinical stage IVA or IVB) or recurrent NSCLC (per Version 8 of the International Association for the Study of Lung Cancer [IASLC] Staging Manual in Thoracic Oncology), not amenable to curative or radiotherapy (e.g., this may occur as systemic recurrence after prior surgery for early stage disease or patients may be newly diagnosed with stage IIIB/IV disease, which is at the start of Osimertinib therapy).
- 6 Patients must have been treated with Osimertinib as first line therapy until disease progression. Evidence of disease progression following 1L Osimertinib can be confirmed by investigators with criteria in Response Evaluation Criteria in Solid Tumours (RECIST) Version 1.1.
- 7 Agree to provide adequate tissue and whole blood for testing after disease progression following 1L Osimertinib.

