### **7.3.1 Collection of Samples for Gene Profile Analysis**

The subject's consent to the use of donated biological samples for research is mandatory at disease progression following 1L Osimertinib in the SoA Samples will be collected from all participants and be used for detecting gene alteration and pathological transformation to explore the whole gene profile post Osimertinib 1L treatment for guiding subsequent treatment strategy.

A unstained, archival tumor tissue sample from a fresh biopsy tissue in a quantity sufficient to allow for gene profile at the time of screening will be collected. Tissue samples will be used for the extraction and analysis of deoxyribonucleic acid (DNA). For the requirement of tissue sample and plasma sample, refer to appendix F.

Whole blood samples (approx. 2\*10 mL) will be taken at disease progression post Osimertinib 1L treatment in the SoA (Table 1). Blood samples to generate plasma samples will be collected from all participants. These samples will be used for the extraction and analysis of circulating tumour deoxyribonucleic acid (ctDNA).

Genetic profiles in tissue and plasma will be analyzed by the central lab NGS testing and then used to analysis positive percentage agreement, sensitivity/specificity of plasma to evaluate concordance between plasma and tissue for exploring whether plasma can be substitute for tissue when patients cannot accept tissue biopsy. The analytical method will be used is described in Section 8.3.2.

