### **8.3.2 Biomarker analysis**

#### **8.3.2.1 Primary Endpoint**

To evaluate the potential molecular resistance mechanism by tissue analysis at disease progression post 1L Osimertinib treatment, tissue samples will be collected at the disease progression. And then the gene profiling of molecular alterations including but not limited to mutations in, amplifications, deletion, fusion and expression of relevant pathway gene will be explored by NGS analysis.

The primary objective is to describe the gene profile in *EGFR*m advanced NSCLC Patients after progression on 1L osimertinib treatment.

Gene profile in tissue will be analysed by NGS method. All gene alterations(e.g., gene mutation, amplification, deletion, fusion, etc.) and histological transformation detected will be observed. Proportion of Gene X alteration(%) = (number of patients with Gene X, which is an example of a certain gene)/(total number of patients in the FAS)×100%. Some cases which patients have more than one gene alteration need to be considered.

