## **Collection of samples for genetic research**

The tissue and blood sample for this genetic research will be obtained from the participants at baseline(disease progression after 1L Osimertinib). Paired tissue and whole blood sample should be collected per participant for genetics during the study.

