
■

■

■

■

■

[figure not shown]

■

□. TIMING OF ALL ANALYSES

Two analyses are planned. The first interim analysis data cut-off (DCO) point will happen when approximately 100 patients have completed their gene testing in tissue and whole blood and got their testing results. The first interim analysis will focus on the primary outcome and secondary outcomes. The final analysis is planned when the last patient has completed their gene testing in tissue and whole blood and got their testing results. The primary outcome, secondary outcomes CCI

will be updated using the data of all patients.

□. CHANGES TO PROTOCOL PLANNED ANALYSES

Changes to protocol planned analyses are summarized as following:

- Added overall percent agreement as a measurement of concordance of NGS in tissue and plasma for secondary endpoint analysis.

□. APPENDIX

□.1 Schedule of Activities

Table 1 Schedule of Activities

Procedure	Screening and Data Collection	Notes	Details in CSP Section or Appendix
Visit	1		
Informed consent ^a	X		Sections 5.1
Inclusion and exclusion criteria	X		Section 5.1 and 5.2
Histology	X		
Clinical stage with lymph node and distant metastasis at diagnosis and post 1L Osimertinib	X		
Record documented common EGFR mutation results by an accredited laboratory through ARMS, Super-ARMS, and NGS testing ^b	X		
Demography and smoking history ^c	X		Section 7.2.1
Physical examination and weight(Kgs)	X		Section 7.2.1
Height(CMs)	X		Section 7.2.1
Medical history and comorbid conditions ^d	X		Section 5.1 and 5.2
WHO/ECOG performance status post Osimertinib 1L treatment	X		Section 7.2.2

Duration of 1L Osimertinib treatment ^e	X		
Best response of 1L Osimertinib	X		
Progression pattern post 1L Osimertinib	X		
Mandatory screening tumour tissue sample (archived or newly acquired biopsy) for Central NGS testing and central MET FISH testing; local IHC testing (included MET overexpression by MET IHC and SCLC pathology transformation by IHC)	X		Section 7.3.1
Mandatory screening blood sample (newly acquired; 2*10ml) for Central NGS testing and central ddPCR MET amplification testing	X		Section 7.3.1 and Appendix C

a Written informed consent and any locally required privacy act document authorisation must be obtained prior to performing any protocol-specific procedures, including screening/baseline evaluations.

b Participants are eligible to be considered for inclusion on the basis of local pre-existing EGFR tumour tissue or plasma testing results by molecular testing.

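### The documents contradict themselves on when the tumour tissue is taken, and the FAS definition has no collection-date condition that would exclude a block taken before osimertinib

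*Protocol*

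**What the plan says.** The places that bear on tissue timing are these.

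- Protocol Table 1 (Schedule of Activities), tissue row: "Mandatory screening tumour tissue sample (archived or newly acquired biopsy) for Central NGS testing and central MET FISH testing". It belongs to the single screening and data collection visit, its Notes cell is empty, and it points to Section 7.3.1. The SAP appendix repeats the row: "Mandatory screening tumour tissue sample (archived or newly acquired biopsy".
- Protocol Table 1, blood row: "Mandatory screening blood sample (newly acquired; 2*10ml". Blood must be new; tissue need not be.
- Note to Table 1: patients are to have a biopsy scheduled after enrolment, and "they will not actually receive a biopsy at the screening visit".
- Protocol 7.3.1, the section the tissue row cites: "A unstained, archival tumor tissue sample from a fresh biopsy tissue", to be collected at screening.
- Protocol 8.3.2.1 (Primary Endpoint): "tissue samples will be collected at the disease progression".
- Appendix C: tissue and blood "will be obtained from the participants at baseline(disease progression after 1L Osimertinib".
- Protocol 7.1 seeks consent for collecting tumour and plasma samples once disease has progressed. The synopsis and Section 4.1 have the paired samples provided after progression.
- Inclusion criterion 7: "Agree to provide adequate tissue and whole blood for testing after disease progression following 1L Osimertinib".
- FAS (Protocol Table 3, SAP 3.1, SAP 5.1): eligible participants with valid gene data from both plasma and tissue. No collection date is mentioned.

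**The concern.** These texts cannot all be followed as written. If no biopsy is done at the only visit, tissue handed over at that visit must already exist. Table 1 allows that without saying how old it may be, and Section 7.3.1 does not settle the matter because it calls the sample both archival and fresh.

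Tissue taken before osimertinib cannot show a change that arose on osimertinib. Such a patient would still count in the FAS denominator, so the frequency of acquired alterations would be understated in the primary endpoint. Pathology transformation has the same denominator and also depends on tissue reflecting the state at progression.

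In the concordance analysis tissue is the reference standard and blood is always new. An acquired alteration correctly found in blood would be scored as a plasma false positive against an old block. SAP 5.4.2 also draws the concordance genes from the 20 most often mutated in tissue, so understated tissue frequencies could alter which genes are assessed.

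The situation is plausible. The protocol itself says tissue was unavailable for some patients after first-line osimertinib, and Section 2.3.1 says the study does not interfere with routine care.

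**Working it through.** **1. The plan's own figures.** Protocol 8.1 and SAP 2.2 give exact (Clopper-Pearson) 95% intervals at N = 200. They reproduce: 40/200 = 20% gives 14.7% to 26.2%, and the rows for 10%, 30%, 40% and 50% also agree. The chance of at least one case at 1% incidence is 1 - 0.99^200 = 86.6%, against the stated 86%. At the 180 expected to yield a profile, the interval for 20% is 14.4% to 26.6%. All of these presume that every tissue sample reflects the state at progression.

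**2. Would any readable rule remove a pre-osimertinib block?**

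- Table 1: no date limit on archived tissue.
- Section 7: routine procedures done before consent may be used if they meet protocol criteria and fall within the time frame in Table 1. Table 1 sets none for tissue.
- Inclusion criterion 7: requires agreement only, and the word after can attach to the testing rather than the sampling.
- FAS: validity of gene data only.
- SAP 4.3.1 and 5.3: neither a tissue collection date nor a tissue-to-blood interval is among the variables listed.

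The sections that tie tissue to progression state an intent. None is turned into a condition for entering the analysis.

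**3. Effect on the primary endpoint.** Let p be the true frequency at progression of an alteration acquired on treatment, and f the share of FAS tissue taken before osimertinib. Assume such tissue lacks the alteration, and that p is the same in patients with old and new tissue. Then:

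expected tissue frequency = p(1-f).

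The documents give no f. The values below are assumptions.

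- p = 7%, the MET amplification rate in the cited single-site tissue study (N = 27): 7% x 0.90 = 6.3% at f = 10%; 7% x 0.80 = 5.6% at f = 20%. The losses are 0.7 and 1.4 points. The exact interval for 14/200 = 7% is 3.9% to 11.5%.
- p = 20%, the planning incidence: 18.0% at f = 10% (36/200, interval 12.9% to 24.0%); 16.0% at f = 20% (32/200, interval 11.2% to 21.8%). At N = 200 the interval around the expected count first fails to cover 20% at f of about 29%.
- f = 0: no effect.

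**4. Effect on concordance.** Take a plasma test that makes no errors about the state at progression.

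- Plasma positive: p. Positive in both: p(1-f). PPV = p(1-f)/p = 1-f, that is 90% at f = 10% and 80% at f = 20%.
- Specificity = (1-p)/(1-p(1-f)). At p = 7%: 0.93/0.937 = 99.3% and 0.93/0.944 = 98.5%.
- Overall percent agreement = 1-pf. At p = 7%: 99.3% and 98.6%.
- Sensitivity = p(1-f)/p(1-f) = 100%, unchanged. The 80% sensitivity mark in Section 4.2.1 is therefore not moved by this mechanism.

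With an imperfect test (assumed p = 20%, plasma sensitivity 80%, specificity 98%), the apparent PPV is 90.9% at f = 0, 81.8% at f = 10% and 72.7% at f = 20%. Apparent specificity is 98.0%, 96.1% and 94.3%.

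**The case against.** The strongest reply is that the protocol, read as a whole, already requires post-progression tissue. Section 7.1 speaks of collection, not testing, after progression. Appendix C equates baseline with progression and asks for a pair. The synopsis and Section 4.1 say the same, and against them the loose reading of inclusion criterion 7 is strained. Archived also has a consistent meaning: a re-biopsy taken at progression in routine care and stored before consent, which would explain an archival sample from a fresh biopsy. SAP 4.3.1 records pathology and gene status at diagnosis separately. The laboratory manual and case report form, which were not available, may contain a date check.

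Most of this stands. A reader might infer that the protocol admits pre-osimertinib tissue by rule. It does not: no section says such tissue is acceptable, and several contradict it. A reader might also infer that acquired alterations will be diluted by a known amount. The documents do not support that either, since they give no f. Nor should the 15% MET and 7% C797X rates quoted in the protocol be used to size a tissue effect, because they come from plasma. The formula also overstates the loss for tissue taken during treatment, which may already carry resistance alterations, and it does not apply to alterations present before treatment, such as the sensitising EGFR mutation.

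What the reply does not answer is that Table 1 is the working schedule for sites, it is the least restrictive text, and the analysis set does not enforce the stricter ones.

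**Conclusion.** The point holds as an internal contradiction that leaves a gap. The intended specimen is post-progression tissue, but the texts disagree on what may be supplied, and nothing in the readable documents excludes an older block from the FAS.

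The size cannot be derived. It is proportional, p(1-f) for a tissue frequency and 1-f for the PPV of an error-free plasma test, and it applies only to alterations acquired on treatment. At the illustrative 7%, shares of 10% and 20% cost 0.7 and 1.4 points, well inside the planned precision. PPV is more exposed, losing 10 and 20 points in the error-free case. If sites supplied only post-progression tissue, both effects are zero, but without a reported collection date a reader of the results could not tell. The conclusion rests on the readable documents alone; a check in the laboratory manual or case report form would narrow it.

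**What to change.** 1. Reconcile Table 1, its biopsy note, Section 7.3.1, Section 8.3.2.1 and the SAP copy of the schedule so that they give one account of the tissue: archived tissue counts only if it was collected at or after progression on first-line osimertinib.
2. Add that collection-date condition to valid tissue data in the FAS definition, in Protocol Table 3 and SAP 3.1, and carry it into SAP 5.1 where the definition is repeated.
3. In the SAP, summarise the interval between tissue and blood collection. Repeating the concordance analysis for pairs within a pre-set interval is optional.

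The cost is wording in both documents, one date check per sample and one summary table. No additional biopsy is asked for. The downside is that a few patients with only older tissue would leave the FAS, with a small loss of precision.
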